11.2.2 Secondary Efficacy Analyses

The first secondary efficacy analysis will be analyzed using the F-S test (Finkelstein and Schoenfeld 1999). This method compares each subject to every other subject in a pairwise manner following the ranking of the first secondary endpoint (Ordinal Outcome Scale):

- 1) not hospitalized and no limitations of activities;
- 2) not hospitalized, with limitation of activities, home oxygen requirement, or both;
- 3) hospitalized, not requiring supplemental oxygen and no longer requiring ongoing medical care
- 4) hospitalized, not requiring supplemental oxygen but requiring ongoing medical care
- 5) hospitalized, requiring any supplemental oxygen;
- 6) hospitalized, requiring noninvasive ventilation or use of high-flow oxygen devices;
- 7) hospitalized, receiving invasive mechanical ventilation or extracorporeal membrane oxygenation (ECMO);
- 8) MI or stroke diagnosed since randomization
- 9) Death

The F-S test is based on the sum of 'scores' of subjects in the CardiolRx™ group. Where the score is 1, -1 or 0 according to whether the subject is the winner, the loser or tied, respectively, according to the hierarchy above.

In addition, the CardiolRx™ to placebo Win ratio (WR) will be calculated, as described by Pocock.(Pocock et al. 2012) For this statistic, every subject in the CardiolRx™ group is compared to every subject in the placebo group in a pairwise manner following the ranking of the first secondary efficacy endpoint. The WR is the number of pairs with CardiolRx™ subject 'wins' divided by the number of pairs with placebo subject 'wins'. The associated 95% CI will be based on the F-S test statistic to ensure consistency between the CI and the F-S test. A 95%CI for the WR entirely above 1 indicates a better outcome in the CardiolRx™ group.

Changes in hs-troponin and TNF-alpha from baseline to peak elevation during the 28-day treatment period between the two treatment groups will be analyzed using an ANCOVA with the baseline value as covariate.

Treatment effect estimates and 95% confidence intervals will be determined.

To control the family-wise Type I error rate, the Benjamini-Hochberg procedure will be applied to all secondary efficacy analyses.

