#### 4.1.4 Secondary Efficacy Parameters

Secondary efficacy parameters include:

-Win Ratio of Ordinal Outcome Scale endpoint:

- 1) not hospitalized and no limitations of activities
- 2) not hospitalized, with limitation of activities, home oxygen requirement, or both;

- 3) hospitalized, not requiring supplemental oxygen and no longer requiring ongoing medical care
- 4) hospitalized, not requiring supplemental oxygen but requiring ongoing medical care
- 5) hospitalized, requiring any supplemental oxygen;
- 6) hospitalized, requiring noninvasive ventilation or use of high-flow oxygen devices;
- 7) hospitalized, receiving invasive mechanical ventilation or extracorporeal membrane oxygenation (ECMO);
- 8) MI or stroke diagnosed since randomization
- 9) death.

- Change in high sensitivity-troponin (hs-troponin) from baseline to peak elevation during the 28-day treatment period
- Change in Tumor Necrosis Factor (TNF)-alpha from baseline to peak elevation during the 28-day treatment period

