#### 4.1.5 Other Efficacy Parameters

Other efficacy parameters include:

- Percentage of patients developing any one of the primary endpoint components within 60 days post randomization
- CV mortality at 28 days post randomization
- Percentage of patients requiring dialysis within 28 days post randomization
- Win ratio of the Ordinal Outcome Scale endpoint within 60 days of randomization
- Patient Impression of Change Questionnaire (PICQ) at Day 28 and at Day 60
- Development of severe lymphopenia, defined as < 1000 cells/ microliter within 28 days post randomization
- Change in (elevation of) hs-troponin, NT-proBNP, D-dimer and in inflammatory markers (hs-CRP, ferritin, TNF-alpha, IL-1 beta, IL-6, IL-10) from baseline to Day 7 (AUC)
- Change from baseline to peak elevation of NT-proBNP, D-dimer and in inflammatory markers (hs-CRP, ferritin, IL-1 beta, IL-6, IL-10) during the 28-day treatment period
- Change from baseline to peak elevation of LDH during the 28-day treatment period
- Difference in cardiac magnetic resonance imaging (CMR) parameters: LVEF, LVEDV, LVESV, LAESV, ECV, GLS, LV mass, LGE extent and edema between the

---

two treatment groups after 4 weeks of study treatment (in a subset of patients at selected sites).

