### 9.2 Secondary Efficacy Analyses

Due to the early termination of the study the Win Ratio of the Ordinal Outcome scale will not be generated. Ordinal outcome scale scores will be listed and summarized for each visit.

The change from baseline in each biomarker (hs-troponin, NT-proBNP, D-dimer) and inflammatory marker (hs-CRP, ferritin, IL-1 beta, IL-6, IL-10) over time will be summarized at each time point and graphically displayed. After review of the profiles over time, the following parameters may be calculated.

Emax 7	Maximum post-baseline change* (baseline-corrected change) up to the time of the Day 7 assessment; reported to 2 decimal places.
Emax 28	Maximum post-baseline change* (baseline-corrected change) up to the time of the Day 28 assessment; reported to 2 decimal places.
AUEC0-7	Area under the change from baseline curve from time zero to the Day 7

AUEC0-28	assessment; calculated using the linear trapezoidal rule; reported to 3 significant figures.
	Area under the change from baseline curve from time zero to the Day 28 assessment; calculated using the linear trapezoidal rule; reported to 3 significant figures.

\*maximum post-baseline change will be positive for biomarkers that increase relative to baseline over the time interval; or negative for those that decrease relative to baseline.

Assumptions for AUEC calculation:

- Time points other than pre-dose will use actual time point instead of nominal time points. If actual assessment time is missing the nominal time will be used.
- Values missing at time points after baseline and prior to last time point in the interval will not be imputed.
- If data at last time point is missing, AUEC will be calculated up to latest non-missing time point.
- AUEC calculation will not include unscheduled and repeat measurements.

Comparison of each parameter between the two treatment groups using an ANCOVA with fixed factors for treatment and the baseline value as covariate will be performed.

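### SAP 9.2 makes the parameters of the only retained tests optional after an unspecified profile review, omits the secondary endpoint TNF-alpha, and conflicts with SAP 10

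*SAP*

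**What the plan says.** Protocol 11.2.2 commits, without conditions, to an ANCOVA with baseline as covariate for "Changes in hs-troponin and TNF-alpha from baseline to peak elevation during the 28-day treatment period". SAP 4.1.4 keeps both as secondary endpoints: "Change in high sensitivity-troponin (hs-troponin) from baseline to peak elevation during the 28-day treatment period" and "Change in Tumor Necrosis Factor (TNF)-alpha from baseline to peak elevation during the 28-day treatment period". SAP 4.1.5 also keeps TNF-alpha among the markers with an AUC endpoint to Day 7.

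SAP 6.2 and 6.4 withdraw all testing because of early termination, except for the bio- and inflammatory markers, and point to Section 9.

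SAP 9.2 lists three biomarkers (hs-troponin, NT-proBNP, D-dimer) and the "inflammatory marker (hs-CRP, ferritin, IL-1 beta, IL-6, IL-10) over time will be summarized at each time point". It continues: "After review of the profiles over time, the following parameters may be calculated". The parameters are Emax 7, Emax 28, AUEC0-7 and AUEC0-28. A footnote adds that the "maximum post-baseline change will be positive for biomarkers that increase relative to baseline over the time interval; or negative for those that decrease". The test is then stated: "Comparison of each parameter between the two treatment groups using an ANCOVA with fixed factors for treatment and the baseline value as covariate".

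On blinding, SAP 2 says the plan is approved before the blind is broken, and SAP 3.2 says the blind is broken after database lock. SAP 2 also says that changes from the protocol are noted. SAP 10, the section on changes, states that there will be no inferential testing, names no exception, and refers back to the limited reporting described earlier.

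**The concern.** The marker ANCOVAs are all the inference left in this trial, so their definition should be the firmest part of the SAP. Instead, which quantities are tested depends on looking at the data, under a rule that the SAP does not give. A plan approved blind that postpones the choice of tested variable has not fixed that variable.

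Three consequences follow. The hs-troponin secondary analysis, unconditional in the protocol, can be left out. The TNF-alpha secondary endpoint has no stated analysis, although the SAP still lists it. For hs-troponin, the quantity that would be tested may not be the endpoint: a peak and a largest decrease are different summaries of the same profile. In addition, someone who consults only SAP 10 would conclude that no test is run.

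**Working it through.** **No plan figure to reproduce.** The SAP gives no alpha, number of tests or error rate for the markers. The sample size of 211 per group concerns the primary endpoint and does not enter here.

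**1. What is left open.** Markers named in SAP 9.2: 3 + 5 = 8. Parameters: 4. Possible ANCOVAs: 8 × 4 = 32. Matched to the endpoint lists in SAP 4.1.4 and 4.1.5:

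| Tests | Number | Status |
|---|---|---|
| hs-troponin Emax 28 | 1 | Secondary |
| Emax 28 of the other 7 markers | 7 | Other efficacy parameter |
| AUEC0-7 of 8 markers | 8 | Other efficacy parameter |
| Emax 7 and AUEC0-28 of 8 markers | 16 | No listed endpoint |

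The total is 1 + 7 + 8 + 16 = 32. The word *may* governs all 32, including the single secondary one.

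**2. Does another section close the gap?** SAP 2 dates approval of the plan and SAP 3.2 dates unblinding. Neither mentions the profile review. It could come before or after unblinding, and could use pooled or by-arm profiles, and still comply with the text.

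**3. TNF-alpha.** It is in SAP 4.1.4 (peak change) and in SAP 4.1.5 (AUC to Day 7), but not in SAP 9.2. The five inflammatory markers in 9.2 are exactly those in the peak-change item of SAP 4.1.5, which rightly leaves TNF-alpha out because its peak change is already secondary. That points to copying from this item. Neither 9.2 nor 10 records a change. Protocol 9.1 schedules frozen samples for TNF-alpha at the same visits as the other markers (baseline and Days 3, 5, 7 and 28).

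**4. Emax against peak elevation.** Take a hypothetical patient whose changes from baseline at Days 3, 5, 7 and 28 are −5, −15, −30 and −45. The highest post-baseline value minus baseline is −5. The largest decrease is −45. Both are negative, so the sign stated in the footnote does not tell the programmer which to use. Only the first is a change to peak.

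**5. Testing statements.** SAP 6.2 and 6.4: no testing except markers. SAP 9.2: marker ANCOVAs. SAP 10: no inferential testing. The last contradicts the other three.

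**6. Illustration of size.** Assumptions, none from the SAP: two-sided 0.05 per test; no treatment effect; normal data at baseline and four later visits; a range of within-marker correlations; AUEC by linear trapezoid; ANCOVA on treatment and baseline. Patient numbers at termination are not given, so arm size was varied.

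| Arm sizes simulated | At least one of four p<0.05 | Emax 28 alone |
|---|---|---|
| 20, 40, 100 | 0.101 to 0.123 | 0.047 to 0.053 |
| 10, 20, 50 | 0.095 to 0.138 | 0.044 to 0.058 |

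Rounded: about 10 to 14% against 5%. Four independent tests would give 1 − 0.95⁴ = 0.186; the figure is lower because the four parameters share data.

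**The case against.** The strongest reply is that this is an abbreviated, descriptive report of a stopped trial, approved blind. Parameters are to be chosen on profile shape, not on p values, and every parameter that is calculated must then be compared. Nothing allows one to be discarded once its p value is known, and SAP 4.1.4 still identifies peak change over 28 days as the secondary quantity. This stands to a point. The documented risk is that Emax 28 is omitted, not that it is selected as the best of four, so the 10 to 14% is an illustration and not a property of the plan.

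On TNF-alpha, the omission may be clerical, the exception in 6.2 and 6.4 covers inflammatory markers in general, and the SAP pages after its reference list were not available for this review. All true; but a slip needs correcting, and an output elsewhere would contradict 9.2. It is also fair that retained samples do not show that TNF-alpha was assayed.

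On the footnote, the wording is about biomarkers, and it may mean no more than that the change carries a sign. That reading is possible, which is why the text needs a definition.

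On SAP 10, its closing sentence sends the reader back to sections that state the exception. This makes it a drafting conflict and not concealment.

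A reader might also infer that dropping the protocol's Benjamini-Hochberg step in SAP 6.4.1 inflates error among the secondary tests. The text does not support this. SAP 9.2 drops the win ratio and omits TNF-alpha, so one secondary test remains, and the procedure applied to one test changes nothing. SAP 6.4.1 states its position openly, and the protocol's family was three endpoints, not two markers.

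**Conclusion.** The concern holds as a defect of specification. Protocol 11.2.2 made two marker analyses unconditional. Under SAP 9.2 one is optional after data review and the other has no stated analysis, and no reason for either is recorded despite the undertaking in SAP 2. The peak is not clearly defined, and SAP 10 conflicts with 6.2, 6.4 and 9.2.

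These conclusions rest on the text alone. The size, about 10 to 14% against 5%, rests on the stated assumptions and also on selection guided by treatment-group results. Two stronger inferences are not supported. The documents do not say that the review is unblinded or that any bias occurred; they leave its status unstated. Nor does the footnote favour a patient-by-patient sign rule, since it speaks of biomarkers that rise or fall.

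**What to change.** Amend the SAP before unblinding:

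- **9.2, parameters.** Change *may be* to *will be* and delete the profile-review condition, at least for Emax 28 of the secondary markers. Alternatively, state that the review is pooled over arms, blinded and completed before unblinding, and give its criterion.
- **9.2, markers.** Add TNF-alpha. If it was not assayed, record in SAP 10 that it is dropped and why.
- **9.2, footnote.** For hs-troponin and TNF-alpha, define Emax 28 as the highest post-baseline value up to Day 28 minus baseline, even if negative.
- **9.2, labels.** Call the other marker parameters exploratory, with nominal p values, in line with protocol 10.1.3.
- **10.** Repeat the marker exception from 6.2 and 6.4.

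The cost is wording only. No extra sampling is needed, though TNF-alpha can be analysed only if the stored samples were assayed. The downside is losing the freedom to drop a parameter that fits the profiles poorly.

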### 6.2 General Statistical Methods and Data Handling

Tabulations will be produced for appropriate demographic, baseline, efficacy, and safety parameters.

Due to the early termination of the study no statistical testing will be performed, with the exception of the bio- and inflammatory marker data (see Section 9). All summaries will be presented descriptively.

Listings will be sorted by treatment and subject ID unless specified otherwise.

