#### **6.4.1 *Multiple Comparisons/Multiplicity***

Due to the early termination of the study no adjustments for multiple comparisons are defined. All summaries will be presented descriptively.

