## 10 CHANGES TO PLANNED ANALYSES

Due to the early termination of the study no inferential testing will be performed. All summaries will be presented descriptively. Limited scope reporting is described above.

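### A missing Day 7 or Day 28 sample shortens the AUEC but leaves its label unchanged, so areas over different intervals enter one ANCOVA

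*SAP*

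**What the plan says.** SAP 9.2 lists four parameters for eight markers (hs-troponin, NT-proBNP, D-dimer, hs-CRP, ferritin, IL-1 beta, IL-6, IL-10). They are conditional: "After review of the profiles over time, the following parameters may be calculated". AUEC0-28 is the "Area under the change from baseline curve from time zero to the Day 28 assessment", by the linear trapezoidal rule, and AUEC0-7 is its counterpart to Day 7. Both are total areas, not averages over time.

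The assumptions listed under the definitions include:
- For a missing end sample: "If data at last time point is missing, AUEC will be calculated up to latest non-missing time point".
- For timing: "Time points other than pre-dose will use actual time point instead of nominal time points".
- Interior gaps are not imputed, and unscheduled or repeat measurements are left out.

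Each parameter is then compared between arms "using an ANCOVA with fixed factors for treatment and the baseline value as covariate".

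SAP 6.2 and 6.4 keep testing for these data only: "no statistical testing will be performed, with the exception of the bio- and inflammatory marker data". SAP section 10 says "no inferential testing will be performed". Protocol 6.2 and Appendix 17.2.2 place the central samples at baseline and Days 3, 5, 7 and 28.

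**The concern.** The missing-sample rule contradicts the definition above it. A total area that stops early is a different quantity from one that runs to the end of the interval. Nothing in either document rescales, relabels, excludes or adjusts for the short areas. Stopping a total area early is the same as adding zero for the unobserved period. That is an unstated imputation of no net change, in a plan whose section 6.6.5 imputes nothing except dates.

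The sampling schedule makes the loss large for AUEC0-28. There is no planned sample between Day 7 and Day 28, and unscheduled samples cannot fill the gap. After Day 7 there are no home visits (Protocol 9.1 and Appendix 17.2.1), so a discharged patient's Day 28 sample depends on an out-patient visit.

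Two consequences follow:
- If end samples are missing equally in both arms and unrelated to outcome, type I error is not inflated, but a real difference is shrunk and power is lost.
- If missingness differs by arm, the estimate shifts and a difference can be created or hidden.

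The markers are the only data for which SAP 6.2 and 6.4 retain a between-group test. Up to 32 ANCOVAs are possible (8 markers × 4 parameters), 16 of them on an AUEC, and "no adjustments for multiple comparisons are defined".

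**Working it through.** The plan gives no figure for the AUECs to reproduce. Its 211 per group is for the primary endpoint and does not enter here.

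**Inputs from the documents.** Samples at Days 1, 3, 5, 7 and 28. With time zero at Day 1, t = 0, 2, 4, 6, 27 days.

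**Interval lost.**
- AUEC0-28 without Day 28, Day 7 present: 27 − 6 = 21 of 27 days (78%). With time zero at Day 0 it is 21 of 28 (75%).
- AUEC0-7 without Day 7, Day 5 present: 2 of 6 days (33%), or 2 of 7 (29%).

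**Area lost.** The trapezoid sums (t_j − t_{j−1}) × (y_j + y_{j−1})/2.
- Assumed plateau, change of +10 from Day 3: 10 + 20 + 20 + 210 = 260 for AUEC0-28. Without Day 28 it is 50 (−81%). AUEC0-7 is 50, or 30 without Day 7 (−40%).
- Assumed marker that crosses baseline (+30, +40, +20, −40): 30 + 70 + 60 − 210 = −50 in full, and 160 without Day 28. The sign reverses.

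**Comparison with allowed visit timing.** The windows in Protocol 9.1 are ±2 days after Day 7 and ±1 day up to Day 7. The plateau areas move only to 10 + 10 × (23 to 27) = 240–280 and 10 + 10 × (3 to 5) = 40–60.

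**Bias with no true effect.** If missingness is unrelated to outcome within arm, bias = difference in missing fractions × mean lost area. No SD is needed. For the plateau with 30% versus 15% missing:
- AUEC0-28: 0.15 × 210 = 31.5, and 31.5/260 = 12%.
- AUEC0-7: 0.15 × 20 = 3, and 3/50 = 6%.

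**Dilution of a proportional effect at equal 20% missing, plateau.**
- AUEC0-28: 0.8 + 0.2 × 50/260 = 0.84, a 16% loss.
- AUEC0-7: 0.8 + 0.2 × 30/50 = 0.92, an 8% loss.

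**Simulation of the SAP's ANCOVA (all inputs assumed).** Mean change −10, between-patient SD 5, residual SD 3, 50 per arm, end samples missing at random, two-sided 5% test:

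| Setting | AUEC0-28 | AUEC0-7 |
|---|---|---|
| No effect, 20% vs 20% missing: rejection | 5.3% | 4.8% |
| No effect, 20% vs 10%: false difference; rejection | 21.6; 12.1% | 2.1; 7.2% |
| No effect, 30% vs 10%: false difference; rejection | 41.6; 28.1% | 4.0; 11.3% |
| True effect −3 units, none missing: estimate; power | −78; 79% | −15.1; 80% |
| True effect −3 units, 20% vs 20%: estimate; power | −65; 52% | −13.7; 71% |

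The false differences agree with the formula: 0.1 × 210 = 21 and 0.2 × 210 = 42 for AUEC0-28, and 2 and 4 for AUEC0-7.

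**Sensitivity to distribution and profile.** A wider set of assumed profiles (sustained, plateau, resolving, crossing baseline) was run for AUEC0-28 with no effect and 30–60 per arm. Type I error under truncation:
- 30% vs 15% missing: about 5–31% for Gaussian data, 4–27% for moderately skewed data and 3–13% for strongly right-skewed data.
- 20% vs 15% missing: 3–8%.
- Equal 20% missing: 3–5%.

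At 60 per arm and 30% vs 15% missing, requiring the end sample gave 3–6%.

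**The case against.** The strongest reply is that little rests on these areas. The rule bites only if the AUECs are calculated, end samples are missing, and the comparison is run despite section 10. The trial stopped early and no confirmatory conclusion depends on an AUEC. AUC to Day 7 is supportive under Protocol 10.1.3, and AUEC0-28 is not a protocol endpoint. The rule is openly stated, changes are summarised and graphed at each time point, and SAP 7.2 tabulates visit attendance. The large error rates need a gap in missingness between blinded arms that nothing in the documents supports, and the effect on AUEC0-7 is smaller. AUEC0-28 collapses to AUEC0-7 only if Day 7 is present; otherwise it stops at Day 5 or Day 3.

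All of that stands, and it limits the severity. It does not remove the defect: stating the rule openly does not make the short areas estimate the defined quantity, and an attendance table does not correct an ANCOVA.

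Requiring the end sample is also imperfect. It drops patients who died or did not attend. When smaller Day 7 falls were made more likely to have a missing end sample, its simulated type I error was 4–10%, against 3–20% for truncation. In one set-up (resolving profile, strongly skewed, 60 per arm) its bias was larger than under truncation (−363 versus −163). A repeated-measures contrast held 3–5% in the same settings.

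**Conclusion.** The concern holds. As written, the rule gives a quantity that does not match its definition, and nothing else in the plan repairs it. The interval loss follows from the sampling schedule alone. The loss of area also depends on the profile, and in the special case where the Day 7–28 area nets to zero, truncation changes nothing but the label. The size of any bias or dilution depends on missing rates that the documents do not give, and the error rates depend further on SDs, distributions and a final sample size that are also not given, so the simulated figures are illustrations.

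This should be fixed before unblinding, but it does not threaten a confirmatory result. If section 10 prevails and no ANCOVA is run, the harm is confined to summaries that mix interval lengths under one label.

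**What to change.** Replace the truncation sentence in SAP 9.2 with: *AUEC0-7 and AUEC0-28 are calculated only for patients with the scheduled end-of-interval sample (Day 7 or Day 28, at its actual time); otherwise that AUEC is missing.* Report the number excluded by arm and reason, including death. State the downside: fewer patients, and possible bias if missingness is informative.

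As an optional alternative or sensitivity analysis, fit a repeated-measures model to all scheduled samples and estimate the fixed-interval difference as a weighted sum of adjusted visit differences. The nominal-day trapezoid weights for Days 3, 5, 7 and 28 are 2, 2, 11.5 and 10.5 for AUEC0-28. For Days 3, 5 and 7 they are 2, 2 and 1 for AUEC0-7. State that it assumes data are missing at random and that nominal days replace actual times in this analysis only. Consider a log scale for skewed markers, noting that the estimate is then an area of log ratios.

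Reconcile section 10 with sections 6.2, 6.4 and 9.2 on whether the marker ANCOVAs will be run.

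The cost is one replaced sentence, a count of exclusions and one reconciling sentence. No new data are needed. The optional model is extra work: one model for each of eight markers. SAP section 2 says the plan will be approved before the blind is broken, so the change fits the existing timetable.

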6.4 Randomization Procedure

Randomization will be accomplished by means of a web-based randomization system and will be stratified by center.

PROPRIETARY AND CONFIDENTIAL

The randomization sequence will be generated by random computerized sequence in blocks of 4.

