11.2.1 Primary efficacy analysis

For the primary efficacy analysis, the proportions of patients experiencing at least one primary outcome event as described in section 10.1.1 in the active group will be compared to the proportions of patients experiencing at least one primary event in the placebo group using Fisher's exact test. The proportions will be expressed as percentages. In addition, the 95% confidence interval for the proportion using exact (Clopper-Pearson) estimates will be provided.

A secondary exploratory sensitivity analysis of the primary endpoint will compare time to the occurrence of the first primary event between the two groups using a Cox proportional hazards model. Kaplan-Meier plots for each treatment group will also be generated.

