## 2 INTRODUCTION

This document describes the Statistical Analysis Plan (SAP) for the CARDIOL 100-03 Protocol (Study to evaluate the Efficacy and Safety of CardiolRx™ in Patients with COVID-19 and Cardiovascular Disease or Risk Factors [LANCER]. This is a multi-center, double-blind, randomized, placebo-controlled, parallel group design, 1:1 randomization study. In total 422 patients will be randomized (1:1) to either CardiolRx™ or placebo.

The design and methods of the CARDIOL 100-03 study are described in detail in the study protocol Amendment 3, dated September 23, 2021. The criteria for evaluation of study results and the analysis populations are defined in section 10 of the study protocol and an outline of the statistical analysis plan may be found in section 11 of the same document. The purpose of this document is to describe the analyses that will be performed in accordance with the protocol in more detail.

As the study was terminated early an abbreviated set of reporting will be generated as described herein. This plan will be approved prior to the breaking of the study blind. Changes from the protocol are noted.

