## 3 STUDY DESIGN

### 3.1 *Randomization Methodology*

Randomization will be accomplished by means of a web-based randomization system and will be stratified by center. The program used is Medidata Rave RTSM. The randomization schedule is generated by an unblinded statistician per the protocol requirements and loaded in the system.

The randomization sequence will be generated by random computerized sequence in blocks of 4.

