## 6 STATISTICAL METHODS

### 6.1 Sample Size Justification

Assuming that 19% of patients qualifying for the study in the placebo group would develop one or more primary outcomes, a treatment effect of lowering the event rate by 50% (i.e. only 9.5% of patients treated with CardiolRx™ would experience a primary outcome event, a two-sided alpha of 0.05 and 80% power, 211 patients per group (422 in total) would be required.

The protocol contained information to consider an adjustment to the sample size. Due to the early termination of the study no sample size re-estimation will be performed.

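### The marker ANCOVA, the only comparison the SAP keeps, leaves out centre, the factor that stratifies randomisation; if centres differ, its tests are mildly conservative

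*SAP*

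**What the plan says.** Protocol 6.4 states: "Randomization will be accomplished by means of a web-based randomization system and will be stratified by center". SAP 3.1 repeats this and adds that the sequence is "generated by random computerized sequence in blocks of 4". Centre is the only stratification factor.

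SAP 6.2 and 6.4 drop all statistical testing because of early termination, except for the bio- and inflammatory-marker data. SAP 9.2 compares those markers between arms "using an ANCOVA with fixed factors for treatment and the baseline value as covariate". Protocol 11.2.2 has the same structure for its two marker endpoints, which "will be analyzed using an ANCOVA with the baseline value as covariate". Neither document puts centre in the model or says why it is omitted.

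For the primary endpoint, Protocol 11.2.1 compares the active arm with patients having "at least one primary event in the placebo group using Fisher's exact test". SAP 9.1.1 replaces this with a listing of events and no analysis.

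SAP 2 says the plan will be approved before the blind is broken. The documents do not give the number or sizes of centres, the between-centre variance, or the number of patients enrolled at termination.

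**The concern.** Blocking within centre nearly balances the arms in each centre, which takes most between-centre variation out of the treatment difference. A model without centre leaves that variation in the residual. Its standard error then describes a less precise design than the one used: intervals are wider than they need be and tests reject less often than 5% under the null.

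The marker ANCOVAs are the only comparisons left and the sample is truncated, so precision is scarce. A centre term chosen after unblinding would be open to the charge of selection. One fixed beforehand would not.

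**Working it through.** **The plan's own figure.** SAP 6.1 gives 19% against 9.5%, two-sided alpha 0.05, 80% power and 211 per group. With pooled variance:

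n = [1.960 × √(2 × 0.1425 × 0.8575) + 0.842 × √(0.19 × 0.81 + 0.095 × 0.905)]² / 0.095² = 211.4

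That is 212 rounded up, and 211 per group gives 79.9% power. The figure reproduces. It involves no centre term and does not concern the markers, for which no power is stated.

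**Ceiling on the effect.** Let ICC be the share of outcome variance, after baseline, that lies between centres. With perfect balance within centres, and ignoring degrees of freedom:

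- reported SE / true SE without centre = 1/√(1 − ICC)
- actual type I error = 2Φ(−1.96/√(1 − ICC))
- for a true difference of 2.8 unadjusted standard errors (about 80% power), power is Φ((2.8 − 1.96)/√(1 − ICC)) without centre and Φ(2.8/√(1 − ICC) − 1.96) with it.

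| Assumed ICC | SE ratio | Type I error | Power without centre | Power with centre | Gain (points, unrounded inputs) |
|---|---|---|---|---|---|
| 0.05 | 1.026 | 4.4% | 80.6% | 81.9% | 1.4 |
| 0.10 | 1.054 | 3.9% | 81.2% | 83.9% | 2.7 |
| 0.20 | 1.118 | 2.8% | 82.6% | 87.9% | 5.3 |

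**Realistic small layouts.** Incomplete blocks and small centres reduce the gain. The next table comes from simulation with blocks of 4 in uneven centres. It compares the planned ANCOVA with one that adds centre and pools centres of fewer than 4 patients. All layouts are assumed. There were 3,000 replicates per cell (2,000 for 200 patients), with Monte Carlo error of about 1 point.

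| Layout | ICC 0 | ICC 0.05 | ICC 0.10 | ICC 0.20 |
|---|---|---|---|---|
| 50 patients, 17 centres | 75.8% to 74.7% | 76.7% to 77.2% | 79.7% to 80.4% | 78.7% to 81.2% |
| 80 patients, 20 centres | 80.3% to 79.7% | 78.5% to 78.7% | 79.7% to 80.9% | 80.6% to 84.3% |
| 80 patients, 19 centres (7 with one patient) | 80.6% to 80.0% | 79.7% to 79.7% | 81.1% to 82.3% | 82.9% to 86.4% |
| 200 patients, 22 centres | not run | not run | not run | 84% to 89% |

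A separate run at ICC 0 gave 78.9% to 77.3% (80 patients, 19 centres) and 79.8% to 79.7% (200 patients). The cost when centres do not differ is therefore 0 to about 2 points.

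At ICC 0.20, null error without centre was 0.032 to 0.039 in that run, and the reported SE was 8-9% above its empirical value. Another run with 80 patients in 19 uneven centres agrees: 0.2223/0.2040 = 1.09. The 200-patient layout in the table put the excess at about 14%. That is above the 11.8% ceiling, so I read it as simulation error. In the 19-centre layout, adding pooled centre brought null error from 0.034 to 0.045.

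**Why pooling is needed.** With unpooled fixed centre effects in 80 patients and 19 uneven centres, the reported SE rises at ICC 0 (0.2250 to 0.2397) and power falls from 78.7% to 72.4%. At ICC 0.10 power falls from 77.9% to 75.4%, and it only breaks even near ICC 0.20 (80.5% to 80.8%). Each one-patient centre uses a parameter and contributes nothing to the treatment comparison.

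**The case against.** **A reader might infer that the primary test is affected too.** The documents do not support this. SAP 9.1.1 cancels the analysis, so no planned result would change. Nor does a power comparison of Fisher's test with a centre-stratified Cochran-Mantel-Haenszel (CMH) test isolate centre. At 211 per group with no centre differences, exact power is 76.8% for Fisher and 80.6% for an unstratified Pearson test. Size at a common 14.25% rate is 0.037 against 0.050. Most of any such gap is therefore Fisher's discreteness. Pearson and CMH differ by about 1 point or less up to a latent ICC of about 0.07, and CMH gains about 1 to 2 points at about 0.16. Fisher's test also has no model standard error that could be too wide.

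**A reader might also take it as established that the marker standard errors are too wide and power is lost.** That depends on between-centre variance, which the documents do not give. A high ICC is not obvious. The markers are assayed at a central laboratory (Protocol 9.2.12.2), which removes differences between local assays, and analysing change with baseline as covariate absorbs more. This stands, and it makes the lower part of the ICC range quite plausible.

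**The stakes are modest.** The marker parameters are only ones that may be calculated, and SAP 6.4.1 drops multiplicity adjustment. SAP 10 even says there will be no inferential testing, which must be reconciled with SAP 6.2, 6.4 and 9.2. This also stands: the issue is efficiency in exploratory comparisons.

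**Centre terms can lose power in a small trial with many small centres.** This is true of unpooled fixed effects. With pooling, the loss is at most about 2 points.

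**Conclusion.** The point holds for the marker ANCOVA only. The analysis omits the one factor used to stratify randomisation and gives no reason. If centres differ, the reported standard errors are too large and the tests mildly conservative. The comparison remains valid, with no bias and no type I inflation.

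The size rests on assumed ICCs, centre layouts and sample sizes:

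- ICC 0.05 or below: negligible
- ICC 0.10: about 1 to 2.5 points of power
- ICC 0.20: about 3 to 5 points, with a reported SE about 8-9% too large and null error of about 0.03-0.04 in small uneven layouts.

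This is a modest gain in precision, worth taking because it is cheap and can still be fixed before unblinding.

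**What to change.** Change the model sentence in SAP 9.2 to:

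*ANCOVA with treatment and centre as factors (centres with fewer than 4 randomised patients pooled into one level, the rule fixed before unblinding) and the baseline value as covariate.*

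The rule uses only counts of randomised patients, so it can be applied without treatment codes or marker results. A random centre effect performed similarly (87.1% against 86.4% power with 80 patients in 19 centres at ICC 0.20), but the SAP should name one model and not leave a choice.

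The cost is one change of wording and a few degrees of freedom, up to about 2 points of power if centres do not differ and the sample is small. The primary endpoint needs no change on this account.
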